4.6 DISCONTINUATION OF THERAPY

OCR therapy must be discontinued for any of the following reasons:

- Life-threatening IRR or serious hypersensitivity reaction
- Active hepatitis B infection
- PML
- Active TB, either new onset or reactivation
- HIV
- Patient becomes pregnant
- Unacceptable toxicity
- Patient election to discontinue therapy (for any reason)

4.7 SUBJECT DISCONTINUATION

Patients may also be withdrawn from the study for any of the following reasons:

- Patient withdraws consent
- Patient is unwilling or unable to comply with the protocol
- Physician's discretion

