3. STUDY DESIGN

3.1 DESCRIPTION OF THE STUDY

This is a multicenter, prospective, open-label Phase IV clinical trial. Patients with relapsing forms of MS, ages 18 to 65, who have received a stable dose of NTZ for 12 or more consecutive months, and have been free of relapses, disability worsening or MRI progression 6 months prior to the transition screening visit will be eligible for the study. After informed consent to participate has been obtained, the patient will have a neurological exam, EDSS, 3T or 1.5T MRI, MSIS-29 and labs done for the screening visit to determine eligibility. 3T or 1.5T brain MRI with and without contrast will be performed with the standard MS protocol. It is preferred that the MRIs are done on a 3T scanner for this trial, but not required. MRIs will be performed with 3mm slice thickness with no gaps between slices. Patients will receive their first dose of OCR 4 to 6 weeks after the last dose of NTZ. Other baseline measures, including EDSS, MSIS-29, and labs will be performed within 4 weeks of screening. A neurological exam, EDSS, and labs will be performed at month 3, month 6, month 9, and month 12. MSIS-29 will be performed at months 6 and 12. MRIs will be performed at screening to determine

eligibility and at months 3, 6, and 12. All adverse events will be reported to the study sponsor. OCR will not be provided by the study; the medication will be supplied through the patient's commercial pharmacy and billed to the patient or the patient's insurance.

Patients will receive OCR 4-6 weeks after their last infusion of NTZ. OCR 300mg IV will be given on Day 0 and repeated with the same dose on Day 14±2. Patients will then receive OCR 600mg IV every 24 weeks.

If discontinuation of study drug occurs, the subject may continue in the trial for observational purposes. If willing to continue, they will complete all visit items moving forward, with the exception of study drug dosing and pregnancy testing (if applicable). If study drug is discontinued and the subject is unwilling to continue in the trial, a premature termination visit will be completed as soon as possible.

The target enrollment is 50 patients from 5 centers. Serious adverse events recorded during the trial will be reported to the study sponsor via Medwatch form.

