If study drug is withdrawn and the patient is unwilling to continue in the trial for observation, complete a premature termination visit as soon as possible. If the patient discontinues from the study for any other reason noted in the subject discontinuation criteria, a premature termination visit must be performed as soon as possible. Patients who were withdrawn from the study for any reason will not be replaced. The following clinical and laboratory evaluations will be performed:

- Vital signs
- Neurological exam
- Relapse assessment
- EDSS
- MSIS-29
- Laboratory assessments: CBC, CMP, Pregnancy test (female only)
- Concomitant medications and adverse events
- Primary reason for discontinuation

Unscheduled Visits

Patients will be instructed to contact their treating physician in the event of a relapse and may be asked to return for unscheduled visit to assess any undesired clinical, or laboratory changes that occur during the study.

- Vital signs
- Neurological exam
- Relapse assessment
- EDSS
- Laboratory assessments: CBC, CMP, Pregnancy test (female only) (if indicated, per treating investigator)
- MRI (if indicated, per treating investigator)
- Concomitant medications and adverse events

Study Withdrawal

If a patient is lost to follow-up, she/he will be withdrawn from the study. Appropriate means of contact to consider lost to follow-up are 3 documented phone attempts and 1 certified letter.

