4.9.5 Missing Data

Demographic information and baseline disease for patients who followed protocol and completed the study, violated protocol, and discontinued the study will be reported separately and compared. The reasons for discontinuing or violating protocol and the patient's time on drug at occurrence will be reported and any influence on the trial results will be discussed. To assess the comparability between centers, summaries will be reported for all patients overall and by study center. Any other irregularities that result in missing data will be fully identified and discussed.

For the per protocol and full analysis sets, missing data due to discontinuation will be incorporated as censored time points in the survival analysis of relapse-free patients and ARR will be calculated using the range of time that the individual was in the study. If interim time points at 3, 6, or 9 months are missing, only the time points available will be used in the survival analysis. No relapse data will be missing at baseline, since only patients relapse free for six months are included. For the Kaplan Meier analyses and

log rank tests stratified by age, gender, EDSS, and center, we expect these patient characteristics to be non-missing. However, if they are missing, a complete case analysis per variable will be used and the number of missing will be reported.

For the analysis of the change in EDSS and MSIS-29, a complete case analysis with per protocol patients will be used.

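### Withdrawal from the study under section 4.7 for non-compliance or at physician's discretion ends the search for relapses, so the primary estimate is biased upward if such exits are related to relapse risk

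*Combined protocol and SAP*

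**What the plan says.** Section 4.7 is permissive and concerns the study rather than the drug: "Patients may also be withdrawn from the study for any of the following reasons". Three reasons follow. The first is withdrawal of consent, which is not at issue. The second is "Patient is unwilling or unable to comply with the protocol". The third is "Physician's discretion", with no criteria attached.

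Section 3.1 treats stopping the drug differently: "If discontinuation of study drug occurs, the subject may continue in the trial for observational purposes". That offer is tied to discontinuation of OCR and does not mention exits under section 4.7.

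For those exits, section 4.5.1 states that "a premature termination visit must be performed as soon as possible". The visit includes a neurological examination, a relapse assessment and the EDSS. The only later contact is a telephone call about 30 days on, whose single listed item is adverse events. Section 3.4 says that MS symptoms are generally not recorded as adverse events. Withdrawn patients are not replaced.

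Section 4.9.5 then applies one rule to the per protocol set and the full analysis set: "missing data due to discontinuation will be incorporated as censored time points in the survival analysis of relapse-free patients".

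**The concern.** The primary result is one absolute proportion, relapse-free at month 12, from a single-arm study (section 3.1: "This is a multicenter, prospective, open-label Phase IV clinical trial"). No control arm shares a bias and cancels it. Kaplan-Meier estimation is valid only if patients censored at a given time have the same later relapse risk as those still followed. Leaving because of non-compliance or at a physician's discretion could plausibly be related to that risk, and the physician may know the MRI findings. Appendix A, note M, has the investigator review the month 6 and month 12 scans before the infusion.

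If a patient leaves and relapses afterwards, the relapse is absent from the primary endpoint in the full analysis set as well. An analysis can bound the effect but cannot recover an outcome that was not collected. Section 3.1 already accepts that follow-up can outlast treatment, and section 4.7 does not carry that principle through.

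**Working it through.** **Inputs.** Section 4.9.6: assumed relapse-free proportion 0.80, lower limit 0.68, 45 evaluable patients, 10% attrition, 50 enrolled. Section 4.9.3: two-sided 0.05 level. Section 4.5.1: month 12 is Day 336. The number of section 4.7 exits, and how many of those patients later relapse, are not in the documents and are assumed below.

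**The plan's own figure.** The two-sided 95% Wald lower limit at n = 45 is 0.80 − 1.96 × √(0.80 × 0.20 / 45) = 0.683. Solving for n gives 1.96² × 0.16 / 0.12² = 42.7, so 43, close to the stated 45. Attrition: 45 / 0.90 = 50. The sample size reproduces and this point does not change it. It also shows what 0.80 to 0.68 is: the target half-width of a confidence interval, not a margin to be tested.

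**What follow-up is lost.** For an exit under section 4.7:

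- Up to the exit: relapses should be captured at scheduled or unscheduled visits, or at the termination visit.
- After the exit: the adverse-event call is not a relapse check, and no section asks for relapse status from the clinical record, although section 4.3 says OCR is prescribed as standard care by the patient's neurologist.
- In the analysis: censored. A non-compliant patient might also be left out of the per protocol set altogether under section 4.9.1, which recovers nothing.

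So only relapses after the termination visit are lost.

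**Bounds if every withdrawn patient is a later relapser.** Take 50 patients and 10 true relapses, so 40/50 = 0.80. Let k of the 10 be censored before their relapse. If censoring precedes all observed events, the estimate is 40/(50 − k). If it follows all of them, the estimate is (40 + k)/50.

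| k | 40/(50 − k) | (40 + k)/50 |
|---|---|---|
| 1 | 0.816 | 0.820 |
| 2 | 0.833 | 0.840 |
| 3 | 0.851 | 0.860 |
| 5 | 0.889 | 0.900 |

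For k = 5 the Wald lower limit moves from 0.80 − 1.96 × √(0.16/50) = 0.689 to between 0.797 and 0.817.

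**Mixed cases, by simulation.** Same 50 patients, with the 10 relapses uniform over 336 days. Five patients leave, which is the whole 10% allowance. A hidden relapser leaves at a uniform time before the relapse; a non-relapser leaves at a uniform time over follow-up. Mean Kaplan-Meier estimate at Day 336:

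| Who the five are | Mean estimate | Bias |
|---|---|---|
| Chosen at random | 0.800 | 0.000 |
| One hidden relapser, four non-relapsers | 0.809 | 0.809 − 0.800 = 0.009 |
| Two hidden relapsers, three non-relapsers | 0.829 | 0.829 − 0.800 = 0.029 |
| Five hidden relapsers | 0.892 | 0.892 − 0.800 = 0.092 |

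The random case is unbiased because 5 × 10/50 = 1 relapser is expected among the five by chance, and Kaplan-Meier allows for that. The bias comes from who leaves, not from the amount of attrition.

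**The case against.** Much of the case on the other side stands.

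- **The termination visit is a real safeguard.** A reader might infer that a deteriorating patient can be removed before a relapse is confirmed. The visit is required promptly and includes the assessments that define a relapse. Patients are also told to contact their physician if they relapse, and unscheduled visits include a relapse assessment and the EDSS. Only later relapses escape.
- **Who decides is not stated.** A reader might infer that the unblinded investigator who rates relapses chooses to end follow-up. Section 4.7 names no decision-maker for non-compliance, unwillingness is the patient's own position, and the text does not identify the physician as the relapse rater. Neither MRI activity nor relapse is listed as a reason for withdrawal in sections 4.6 or 4.7.
- **The large figures are extremes.** A reader might take 0.85 or 0.89 as the expected result, or compare a 5-point shift with a 12-point margin. Those values need every withdrawn patient to be a hidden relapser, for which the documents give no basis, and the 12 points are a precision target.
- **Some handling exists.** Date and cause of discontinuation are collected, and sections 4.9.1 and 4.9.5 promise to report reasons and discuss any influence. This is useful for interpretation, but it is descriptive and supplies no missing outcomes.
- **Loss to follow-up is treated reasonably.** The rule "If a patient is lost to follow-up, she/he will be withdrawn from the study" comes with three telephone attempts and a certified letter, and is not criticised here.
- **Follow-up cannot be forced.** A patient unwilling to take part cannot be made to continue, and section 3.3.1 requires objective worsening on the EDSS or functional systems, which a call or chart may not show. The fix has to allow for both.

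What remains is the gap between sections 3.1 and 4.7: a patient who would agree to be observed may be taken out of the study and is then not asked about relapse again.

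**Conclusion.** The point holds as a gap in conduct with a conditional bias. Sections 4.7, 4.5.1 and 4.9.5 together allow relapse follow-up to end for reasons other than withdrawn consent or loss of contact, with censoring in the primary analysis. The bias is upward only if these exits are related to relapse risk; if they are unrelated, it is zero.

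With all five patients of the attrition allowance leaving and a true value of 0.80, one or two hidden relapsers move the estimate by about 0.01 to 0.03. About 0.09 is the extreme. These sizes rest on assumed numbers of exits and uniform timing. The documents do not show that biased withdrawal is likely, only that the plan does not guard against it. The change is a worthwhile, inexpensive improvement, and it leaves the sample size as it is.

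**What to change.** **Section 4.7.** Extend the section 3.1 observation option to exits for non-compliance or at physician's discretion. Relapse follow-up then continues to month 12 for patients who agree, and ends only on withdrawal of consent, loss to follow-up or death. Decisions about OCR stay with the investigator.

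**Section 4.5.1.** For patients who stop attending, obtain relapse dates from the medical record to Day 336 where consent allows.

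**Sections 4.9.3 and 4.9.5.** State how such relapses are counted: in the primary analysis only if the record documents the objective worsening required in section 3.3.1, with other reported relapses included in a sensitivity analysis.

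**Cost.** A few extra contacts or chart reviews for about 5 patients (50 × 10%), one line in the consent form, and an amendment that section 3.5 requires to be approved by the Providence IRB and each site's IRB or ethics committee. Some patients will still decline, so the gap is reduced rather than closed.

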4.8 STUDY DISCONTINUATION

Genentech Study Center, and the Principal Investigator has the right to terminate this study at any time. Reasons for terminating the study may include the following:

- Patient enrollment is unsatisfactory
- Data recording are inaccurate or incomplete
- Study protocol not followed

4.9 STATISTICAL METHODS

4.9.1 Analysis of the Conduct of the Study

The following documentation will be collected and analyzed for all enrolled patients in order to maintain the integrity of the study:

- A. Enrollment date and time
- B. Demographic information
- C. Baseline disease status
- D. If applicable, protocol violation date and cause
- E. If applicable, discontinuation date and cause

Demographic information and baseline disease for all enrolled patients, those who violated protocol, and those who discontinued will be summarized and reported separately. The reasons for discontinuing or violating protocol and the patient's time on drug at occurrence will be reported and any influence on the trial results will be discussed. To assess the comparability between centers, summaries will be reported for all patients overall and by study center. Any other irregularities that result in missing data will be fully identified and discussed.

All patients that followed protocol will be used to evaluate efficacy, safety, and tolerability. This includes patients that discontinued but followed protocol up to discontinuation.

4.9.2 Analysis of Treatment Group Comparability

Not applicable

4.9.3 Efficacy Analysis

a. Primary Endpoint

Proportion of patients relapse free at 12 months after switching from NTZ to OCR

b. Secondary Endpoints

- Proportion of patients relapse-free at 3, 6, and 9 months after switching to OCR
- Mean time to first relapse
- MRI evidence of MS disease activity
- Proportion of patients with New or Enlarging T2 lesions at 3, 6, and 12 months. For patients with New or Enlarging T2 lesions, number of New and Enlarging T2 lesions.
- Proportion of patients with New Gd+ lesions detected at months 3, 6, and 12. For patients with New Gd+ lesions, number of New Gd+ lesions
- Annualized relapse rate (ARR)
- Change in EDSS from baseline to 12 months
- Change in MSIS-29 from baseline to 6 and 12 months

All patients that followed protocol will be used to evaluate the proportion of patients relapse-free at 3, 6, 9, and 12 months, mean time to first relapse, and ARR. This includes those that discontinued early but followed protocol up to discontinuation. All patients that followed protocol and did not discontinue will be used to evaluate MRI

evidence of MS disease activity at 3, 6, and 12 months, the change in MSIS-29 from baseline to 6 and 12 months, and the change in EDSS from baseline to 12 months.

A full analysis set consistent with the intent-to-treat (ITT) principle will also be used to analyze the proportion of patients relapse-free at 3, 6, 9, and 12 months, mean time to first relapse, and ARR using all subjects. Subjects who entered the trial and did not meet inclusion criteria may be excluded.

Summary statistics will be presented for continuous variables (mean, standard deviation, median, range) and categorical variables (counts and percentages). All analyses will use two-sided confidence intervals and p-values at the 0.05 significance level.

Primary Analysis

Kaplan-Meier survival analysis methodology will be used to determine the proportion of patients relapse-free at months 3, 6, 9, and 12. Median and mean time to first relapse with confidence intervals will be reported. Log rank tests and graphical presentations of Kaplan Meier curves with confidence intervals will be used to examine effects of center, gender, categorized age, categorized EDSS and duration of disease on survival distribution.

Secondary Analysis

ARR will be analyzed with a Poisson or negative binomial analysis with the total number of relapses as a dependent variable and the logarithm of time followed as an offset. The number of new or enlarging T2 and Gd+ lesions at 3, 6, 9, and 12 months will be summarized and reported. The mean and median change in EDSS from baseline will be determined at 12 months and tested by Wilcoxon signed-rank tests. The mean and median change in MSIS-29 from baseline will be determined at 6 and 12 months and tested by Wilcoxon signed-rank tests.

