3.2 RATIONALE FOR STUDY DESIGN

The clinical data from OPERA I and II demonstrated a highly efficacious medication with a significant reduction in relapses, MRI progression, and disability progression. In addition, the data suggest that OCR is well tolerated as only 3.2% of patients withdrew secondary to side effects in OPERA I and 3.8% of patients withdrew in OPERA II. From a safety perspective, no opportunistic infections were seen in the clinical trials, and this includes PML.

NTZ is a highly effective medication for treating patients with relapsing MS. However, despite adequate disease control and JCV status, patients will eventually discontinue secondary to the potential risk of PML^{xv}. Unfortunately, multiple studies have demonstrated an increase in risk of disease progression after switching to another agent after discontinuing NTZ^{xvi, xvii, xviii}. So, given the robust clinical data and safety profile from the pivotal OCR trials, this medication is an attractive option for patients and clinicians.

In this clinical trial, patients will receive the FDA approved dose and frequency of OCR. In the RESTORE trial, NTZ concentrations reached undetectable levels 8 weeks after the last infusion. Also, data from several clinical trials including STRATEGY and SWITCH suggest that a shorter washout period will reduce the risk of disease recurrence^{xix}. Therefore, OCR will be infused at a minimum of 4 weeks after the last dose of NTZ and up until 6 weeks.

Measuring breakthrough disease to date is best evaluated by measuring clinical and radiographic changes. A patient outcome measure, MSIS-29, will help evaluate changes in quality of life after transitioning to OCR.

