4.3. STUDY TREATMENT

Patients will be initiated on OCR after informed consent and screening assessment have been completed. The first dose of OCR will be administered between 4 and 6 weeks after the last dose of NTZ. OCR will be prescribed by patient's neurologist as standard of care and paid for by the patient/patient's insurance.

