4.4 CONCOMITANT AND EXCLUDED THERAPY

All concomitant medications are allowed except immunosuppressants, lymphocyte-depleting agents, or lymphocyte-trafficking blockers while patients are receiving OCR. All medications including over-the-counter medication and supplements will be recorded at each clinical visit. At screening, all medications taken 4 weeks prior to screening will be reviewed and recorded, as well as all prior lifetime MS disease modifying therapies taken by the patient.

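### The primary relapse analysis leads with an undefined protocol-adherent set; the full analysis set comes second, has discretionary exclusions, and neither is named primary

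*Combined protocol and SAP*

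**What the plan says.** Section 4.9.1 sets the general rule: "All patients that followed protocol will be used to evaluate efficacy, safety, and tolerability". Section 4.9.3 repeats it for the primary endpoint and the other relapse endpoints: "All patients that followed protocol will be used to evaluate the proportion of patients relapse-free at 3, 6, 9, and 12 months". It then keeps compliant early discontinuers: "This includes those that discontinued early but followed protocol up to discontinuation".

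The second set follows in the same section: "A full analysis set consistent with the intent-to-treat (ITT) principle will also be used to analyze the proportion of patients relapse-free". It covers the same time points, time to first relapse and the annualized relapse rate (ARR), and is meant to use all subjects. It carries one qualification: "Subjects who entered the trial and did not meet inclusion criteria may be excluded".

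The Primary Analysis paragraph of 4.9.3 specifies Kaplan-Meier estimation without saying in which set. Section 4.9.5 censors at discontinuation in both sets. Sections 4.9.1 and 4.9.5 ask for the reasons and timing of violations and a discussion of their influence on the results. No section lists the deviations that remove a patient from the followed-protocol set.

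**The concern.** The order of the two statements in 4.9.3, and the word that introduces the second, make the followed-protocol set the lead analysis. Nothing says which result is the headline or what happens if the two disagree. Treatment is open-label and 4.9.2 confirms that there is no comparison group, so whatever selection occurs goes straight into the single estimate.

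Membership could depend on outcome or prognosis in two ways.

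- **Barred therapy.** Section 4.4 says: "All concomitant medications are allowed except immunosuppressants, lymphocyte-depleting agents, or lymphocyte-trafficking blockers while patients are receiving OCR". It makes no provision for a barred agent given because of a relapse. A patient who relapses, receives such an agent and stays on ocrelizumab (OCR) could be classed as a violator, and the relapse would leave the set. The allowance for discontinuers does not cover this patient.
- **Late switching.** Section 4.3 says: "The first dose of OCR will be administered between 4 and 6 weeks after the last dose of NTZ". Sections 3.1 and 4.3 have the drug paid for by the patient or insurer, so the date of the first dose is partly outside the study's control. The data cited in Section 3.2 "suggest that a shorter washout period will reduce the risk of disease recurrence" after natalizumab (NTZ). Dropping late switchers would narrow the population toward patients whom the protocol itself expects to do better.

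The full analysis set is not a firm backstop while exclusion from it is optional, with no rule on evidence, timing or decision-maker.

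**Working it through.** **Inputs.** From Section 4.9.6: assumed relapse-free proportion 0.80 at 12 months, lower bound 0.68 with 95% confidence, 45 evaluable patients, 10% attrition, 50 in total. From 4.9.3: two-sided 0.05. The documents give no violation rate and no relapse rate among violators, so the counts of excluded patients below are assumptions shown as a range.

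**Step 1: the plan's own figure.** With the Wald precision formula, n = z²p(1−p)/(p−L)² = 1.96² × 0.80 × 0.20 / 0.12² = 42.7, so 43, within 2 of the stated 45. At n = 45 the Wald lower limit is 0.80 − 1.96 × √(0.16/45) = 0.683. Attrition: 45/0.90 = 50. The stated figures are reproduced closely, and they do not depend on which set is primary.

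**Step 2: full set at the planned rate.** Suppose 40 of 50 are relapse-free and nobody is censored before month 12, so that Kaplan-Meier equals the simple proportion. The estimate is 40/50 = 0.800 and the lower limit 0.80 − 1.96 × √(0.16/50) = 0.689.

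**Step 3: the followed-protocol set.** Exclude 5 of these 50, of whom j relapsed. The relapse-free count left is 40 − (5 − j), out of 45.

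| Relapsers among the 5 | Estimate | Shift from 0.800 | Wald lower limit |
|---|---|---|---|
| 0 | 35/45 = 0.778 | −0.022 | 0.656 |
| 1 | 36/45 = 0.800 | 0 | 0.683 |
| 2 | 37/45 = 0.822 | +0.022 | 0.711 |
| 3 | 38/45 = 0.844 | +0.044 | 0.739 |
| 5 | 40/45 = 0.889 | +0.089 | 0.797 |

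**Step 4: general form.** If a share f is excluded and a proportion s of the excluded are relapse-free, the followed-protocol estimate is (p − f·s)/(1 − f). With p = 0.80 and f = 0.10:

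- s = 0.8: (0.80 − 0.08)/0.90 = 0.800
- s = 0.5: (0.80 − 0.05)/0.90 = 0.833
- s = 0: 0.80/0.90 = 0.889

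With f = 0.20 the limits are (0.80 − 0.20)/0.80 = 0.750 and 0.80/0.80 = 1.000. The shift is upward only when s is below p, that is, when excluded patients relapse more often than retained ones.

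**The case against.** The strongest reply is that both analyses are already committed. The full analysis set is planned for the same relapse endpoints in the same section, censored in the same way, and violators are to be described and their influence discussed. That stands. A reader might infer that only protocol followers will be analysed; 4.9.3 contradicts this.

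A reader might also infer that patients are removed because they relapse. No section does so. A patient who relapses, stops OCR and then changes therapy has discontinued after complying, stays in, and the relapse counts as an event. The barred-therapy route is narrow: the agent must be given while OCR continues. Corticosteroid use cannot simply be assumed to create a violation either, because Section 3.4 itself cites the recommendation of methylprednisolone before each infusion.

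Late switching is the weaker route. A late first dose is known at Day 0, before any outcome on OCR, so excluding it changes the population described and is not selection on outcome. The 4-to-6-week window is not among the inclusion criteria in 4.1.2, so the optional exclusion would not take these patients out of the full analysis set. Section 3.2 gives no figure for risk just beyond 6 weeks, and a first dose before 4 weeks would also be a deviation, with the opposite expected effect.

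None of this supplies a definition of following the protocol, a rule for judging it, or a named primary set. Describing violators afterwards makes the selection visible but does not settle which estimate is the headline.

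**Conclusion.** The point holds as a gap in definition and primacy: the plan leads with an undefined set that can be settled after outcomes are known, and leaves the set with the better claim in second place with optional exclusions. It should be fixed, but it does not invalidate the design.

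The size is conditional. With 5 of 50 excluded from a trial that is 0.80 relapse-free overall, the headline moves by between −2.2 and +8.9 percentage points. This rests on the assumed number excluded and on no censoring before month 12. That the estimate is biased upward is a stronger reading which the documents do not support, because they give neither the violation rate nor the violators' relapse rate.

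A reader might also infer that the choice of set decides whether the trial succeeds. Counts can be found that straddle 0.68: with 13 relapses in 50, 4 of them among 5 violators, the full set gives 37/50 = 0.740 (Wald lower limit 0.618) and the followed-protocol set 36/45 = 0.800 (0.683). But 0.68 appears only as a precision target in 4.9.6, and 4.9.3 sets no success rule against it. Those counts also need 4/5 = 80% of violators to relapse against 9/45 = 20% of the others, for which the documents give no basis.

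**What to change.** In 4.9.3:

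1. Name the full analysis set as primary for the relapse-free proportion, time to first relapse and ARR, and say so in the Primary Analysis paragraph. Define it as every enrolled patient who received any OCR, whatever the NTZ-to-OCR interval or later deviations.
2. Replace the optional exclusion with one fixed exception: failure of an entry criterion, shown by data dated before Day 0 and decided before outcome data are reviewed.
3. Report the followed-protocol set as a sensitivity analysis, with the disqualifying deviations listed before outcome review.

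Section 4.9.1 should be brought into line. It also limits the safety evaluation to patients who followed protocol, whereas 4.9.4 summarises adverse events for all patients; the two need reconciling.

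The cost is wording only. Both sets are already planned, no extra data are needed and the sample size is unchanged. The downside is that the headline proportion may be slightly less favourable.
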